person's experience and feedback can be readily obtained. Voice recognition and voice activation furthermore allow non-intrusive and effective ways to capture data on subjects' experiences.

In this study, we want to investigate environmental factors such as light, sound, temperature, smell and sensory experiences such as vibration in patients scheduled for imaging examinations, accompanying individuals, staff working in healthcare environment and volunteers.

We plan to implement innovative methodologies to create different environmental experiences and use response assessment technologies ranging from verbal or tactile feedback to questionnaires.

In the subpopulation of patients that receive imaging examinations, we want to correlate observational findings with image quality of the imaging examination performed and with patient based feedback on responses.

The goal of these exploratory efforts will be to also serve as guidance to develop confirmatory clinical trials that eventually may facilitate and/or encourage refinements of facility environments and patient staff facility interactions to further improve the quality.

IV. Procedures

Research Design

A. Sample

We intend to include the following discreetly different populations in our assessment

Volunteer population

1. volunteers agreeing to complete an electronic survey tool to assess the perception and preference of environmental factors (virtual participation)
2. volunteers agreeing to complete the above survey and participate in environmental experiences and providing feedback about their experience (physical participation)

Staff population

3. staff working in imaging related healthcare environments completing survey tools regarding their perception and preference of environmental factors and participating in environmental experiences by providing feedback.

Patient population

4. patients that agree to complete a survey tool and either participate in specific environmental experience testing or may be exposed to an environment experience during the imaging examination. The imaging exam will be assessed in regard to quality factors such as motion artefacts as an indicator of being relaxed during the examination.

Inclusion Criteria

Volunteer population

- Male and female volunteers above the age of 18 who are able to give an informed consent or have a legal guardian able to give informed consent on their behalf

Staff population

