- Male and female staff at the Ohio State University above the age of 18 who are able to give informed consent

Patient population

- Male and female patients greater than or equal to 18 years of age able to give informed consent or have a guardian able to give informed consent on their behalf
- Must have an imaging study such as an MRI, PET/CT, or CT scheduled to be performed at the Wright Center facility at Martha Morehouse

Exclusion Criteria

- Unable to communicate in English
- Subjects that are incapable of giving informed consent or that do not have a legal guardian to give informed consent.
- Prisoners
- Below age of 18.

A. Measurement / Instrumentation

All tools and devices will be operated according to the manufacturer instruction manual. If consumer grade devices do not have instruction manuals on how those are to be used or applied, the instruction manual for the exploratory testing will be put in place prior to such uses.

Survey tools

We will use survey tools that may either be in paper or electronic form such as SurveyMonkey or similar web app-based technologies. Surveys will by default be completed electronically that can be accessed with a link or will be available on tablets at the facility. As a default, participants will be expected to complete the service tools by themselves; however, participants that may not have the ability to fill out or complete the survey tools may be assisted by a person of their choice (family member, accompanying person) or member of the study team serving as a transcriptionist to only record the responses without biasing.

An open public participation survey will be released upon approval of this study that will allow us to get a general sense of how people would feel about the implementation of these environmental factors in a health care facility. This survey will be posted through online social media. This includes potential advertising on specific online university venues such as OSU onCampus today. This trial will also be posted on clinicaltrials.gov, Research Match, or other trial information databases.

Quality review of the imaging study to evaluate the presence of artifacts

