We will explore the use and linkage of voice activation system such as Amazon Echo, Google home or similar devices. Some participants may be asked to use voice activations to verbally select and/or change the environmental settings according to their preferences. We are evaluating the feasibility of voice activation with the imaging environment.

Temperature monitoring

We will use infrared detector camera technology to assess the skin temperature of subjects at different body regions and changes during the observational period. This will also be used to determine the temperature of the surroundings as well, for example, to determine the relative temperature of the chair and the imaging bed. Infrared cameras installed alongside the normal surveillance cameras to monitor patients during the imaging examination may also be used to monitor the temperature of the surroundings as well as the body to determine if that may be the reason for motion.

Short wave radar

We will use short wave radar to perform positional monitoring of subjects during the observational period. This short-wave radar will be used as a means to assess motion and detect subject movement in a room that we hope to correlate to their level of comfort and relaxation. Short wave radar is also technically able to detect very minuscule motion including blood flow and pulse rate,

which would allow us to move away from wearable devices to remote sensing devices further hoping to increase patient comfort. No short wave radar devices will be used during the imaging examination.

The levels of electro-magnetic field that are being used are at no risk and below the level of mobile phones. The radar sensors are of the technology that are found on self or assisted driving cars. Some studies have found that long-term, consistent exposure to short wave radiation over the course of several years may have negative effects on the central nervous system, cardiovascular system, and endocrine system. However, considering that in this study, exposure to short wave radar is limited to less than a few hours, this risk is insignificant.

Wearable devices

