We will explore the use of wearable devices like Fitbit, Apple Watches, and Samsung Gear Fit devices, which allow the recording of motion and heart rate. Specifically, the following devices may be used during the study: Fitbit Flex 2, Fitbit Alta, Fitbit Alta HR, Fitbit Charge 2, Apple Watch Series 3, Samsung Gear S3, Samsung Gear S4, Samsung Wing, Samsung Gear Edge. Since this is an exploratory study, we will assess the feasibility of using these devices within the study's methodological parameters. This will allow us to determine which devices to use in the experimental trials.

These devices will be placed on the subject at their preferred wrist location and will be removed before leaving the facility. We hypothesize for example that tracking the pulse rate will be an indirect measure of the subjects' excitement level and may also be a ready measurement of the likelihood of motion during an examination. These wearable devices will not be used during the MRI imaging examination.

B. Detailed study procedures

Subject enrollment

As detailed already above, there will be three different populations enrolled in this study, volunteer, staff, and patients. All subjects will sign an informed consent form, and patients are additionally asked to sign a HIPAA waiver.

As part of the informed consent process, the subject identification document will be created that will identify the subject name and current contact information.

In case of patients, their medical record number, referring physician for the imaging procedure performed and contact information of a healthcare provider of their choice if they indicated that any incidental finding should be communicated directly to their healthcare provider, will be recorded.

This document will also record if the subject received a gift card and the amount.

The subjects participating in this research **may be enrolled at multiple times** and can also be involved in multiple subject categories. Multiple enrollment may occur for the purpose of longitudinal observations or assessment after healthcare treatments. The initial and follow up responses may be evaluated regarding changes over time.

Subject Recruitment

Virtual participation only

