Patients may be invited to participate if they are scheduled to get an imaging exam at the Wright Center facility. This means we would look at the schedule of patients expected for an imaging examination at the Wright Center of Innovation. When the imaging exam is scheduled or when they arrive at the facility patients may be asked if they are interested in participating in this research study. Very frequently we communicate prior to an imaging study with the patients, and we may make them aware that there is a possibility for them or also an accompanying person to participate in this research. We assume that we will also be informed from healthcare support staff of referring and collaborating healthcare providers that patients identified their interest to participate in the study. Frequently, patients also contact us as we are the communicated contact pathways identified on brochures and others posts and we will subsequently follow-up and discuss potential participation. Not every patient will be approached regarding this study, we will have to determine the feasibility in the schedule and determine if we have the staff on hand to complete the study, additionally, what imaging examination they get may also determine if at the time they can enroll in the study or not.

Administration of informed consent

Informed consent may be given at any time after the subject had appropriate time to read the informed consent form and ask and receive answers to any questions. As we anticipate that, for example, accompanying persons waiting for patients to complete their imaging study may be willing to participate in this study. Therefore, we may approach a subject immediately prior to the opportunity to participate especially as this is a minimal risk investigation. We have prepared a video that explains this trial to interested subjects. The video link may also be referenced in advertising material and brochures.

We prepared a training video for the trial staff to see how we would like to have the informed consent administered according to all aspects of GCP and applicable guidelines. There are different videos for each the patient, staff and volunteer populations.

The informed consent form may be given to subjects ahead of time. There will be online access to the informational video and the informed consent forms.

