Environmental Experience	
Lighting	
Sound	
Smell	
Vibration	
Temperature	
Voice activation	
Observational Tools	
Surveys	
Infrared Camera	
Radar	
Wearable device	

Location of performance of research

Due to the simplicity of the set up and straight forward design of this research it can be performed whenever subjects are available at the Wright Center facility; however, trained personnel will also have to be available.

While the patient related research efforts will be exclusively performed at the Martha Morehouse facility at The Ohio State University Wexner medical center, staff and volunteer environmental experience could be performed anywhere on the OSU campus or its affiliated facilities.

The online survey can be performed anywhere and the location will not be tracked.

Testing procedures and data recording

As we intend to develop research testing procedures tailored to the specific environmental experience or observational tools, we plan to refine the specific forms and assessment protocols in an iterative fashion during the initial phase that will include up to 25 subjects for each of the environmental experiences. The initial survey tools have been put in place and are available.

RP0525 Testing Procedure: Survey Tools

General Survey

The general survey that we intend to release via online social media for the public to take. This is the survey that will be openly accessible to the public and will be posted online for the virtual participation:

[**RP0525_EnvironmentalFactorsSurvey_SurveyMonkey.pdf**](#)

This can be accessed with the link: <https://www.surveymonkey.com/r/environmental-perception>

Study Survey

The survey tool that will be used to collect data from the subjects. Note that there is circular logic applied making sure all the data is combined into one database although no subject will actually complete every question.

[RP0525_EnvironmentalFactorsStudy_SurveyMonkey.pdf](#)

This can be accessed with the link:

https://www.surveymonkey.com/r/RP0525_EnvironmentalStudy

Imaging Assessment Survey

The survey completed by imaging assessors to determine the level of motion artefacts present in the images:

[RP0525_ImagingAssessmentSurvey_SurveyMonkey.pdf](#)

This can be accessed with the link:

https://www.surveymonkey.com/r/RP0525_ImagingAssessment

Incidental findings

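### Does Aim 3 confound environment with scan type by pooling MRI, PET/CT and CT?

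*Protocol*

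**What the plan says.** The patient inclusion criteria name the scan types as an open list: "Must have an imaging study such as an MRI, PET/CT, or CT scheduled to be performed". Section IV.A (Sample, Patient population) gives the reason for scoring the scans: "The imaging exam will be assessed in regard to quality factors such as motion artefacts as an indicator of being relaxed during the examination". Section III states the intended relation: "we want to correlate observational findings with image quality of the imaging examination performed". Under Testing procedures and data recording, one assessment form is listed, described as "The survey completed by imaging assessors to determine the level of motion artefacts present in the images". The form is a linked file and its items are not reproduced.

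Three further statements bear on scan type:

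- Subject Recruitment, Patient Population, after mentioning scheduling and staffing: "what imaging examination they get may also determine if at the time they can enroll in the study or not".
- Wearable devices: "These wearable devices will not be used during the MRI imaging examination".
- Short wave radar: "No short wave radar devices will be used during the imaging examination".

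On analysis, the section Data analysis and analytics says that, for want of prior data, no detailed plan has been developed. It foresees descriptive statistics and an exploration of relationships, with statistical advice taken along the way. Section D (Data Analysis) repeats that only descriptive methods are intended for now. The Internal Validity section lists confounding, selection bias and temporal precedence among the threats to be assessed.

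**The concern.** Motion artefacts are given one meaning, relaxation, with no mention of scan type. A long MRI and a short CT need not be equally prone to motion. The protocol also lets the type of exam influence who is enrolled, and it bars wearables during MRI without stating the same for CT or PET/CT. In-scan exposure is optional and not assigned.

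Together these suggest that a correlation of exposure or pulse with artefact score, taken over all patients, would partly compare MRI with CT, and partly compare pulse readings taken outside the scanner with readings taken inside it. Aim 3 is the only aim tied to image quality, and its results are meant to guide confirmatory trials. A spurious or reversed association there could send those trials in the wrong direction.

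**Working it through.** **1. What the plan's own figures give.** The protocol states no power, significance level or effect size for Aim 3, so there is no figure of that kind to reproduce. The enrolment split is consistent: 125 + 125 + 250 = 500. With the stated 20% loss, 125 × 0.80 = 100 patients would have complete data. The protocol does not itself name 100 as a target.

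**2. How large pooling bias could be.** The protocol gives no scan mix, artefact rates or exposure rates, so every input here is an assumption: 50 MRI and 50 CT patients, artefacts in 30% of MRI and 5% of CT scans, exposure in 60% of MRI and 30% of CT patients, and no effect of exposure within either type.

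- Exposed (30 MRI, 15 CT): (30 × 0.30 + 15 × 0.05)/45 = 9.75/45 = 21.7%.
- Unexposed (20 MRI, 35 CT): (20 × 0.30 + 35 × 0.05)/55 = 7.75/55 = 14.1%.
- Difference +7.6 points, ratio 1.54.
- Exposure reversed (30% of MRI, 60% of CT): (4.5 + 1.5)/45 = 13.3% against (10.5 + 1.0)/55 = 20.9%. Difference −7.6 points, ratio 0.64.

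Ends of a wider range:

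- Artefacts 20%/10%, exposure 60%/30%: 7.5/45 − 7.5/55 = 16.7% − 13.6% = 3.0 points.
- Artefacts 40%/5%, exposure 70%/20%: 14.5/45 − 8/55 = 32.2% − 14.5% = 17.7 points.

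**3. The same on the correlation scale.** Let p be the MRI share. Let a and b be the MRI-minus-other shifts in exposure (or sensor value) and in artefact score, in within-type standard deviations. With no correlation within type, the pooled correlation is

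r = a·b·p(1−p) / √[(1 + a²p(1−p))(1 + b²p(1−p))].

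| a, b | r for p from 0.2 to 0.7 | chance of nominal 5% significance, n = 100 |
|---|---|---|
| 0, 1 | 0 | 5% |
| 0.25, 0.5 | 0.02–0.03 | 5–6% |
| 0.5, 0.5 | 0.04–0.06 | 7–9% |
| 0.5, 1 | 0.07–0.11 | 11–19% |
| 1, 1 | 0.14–0.20 | 28–52% |

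For scale, the 95% confidence interval around r = 0 has a half-width of about 0.20 at n = 100.

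**4. What the bias needs, set against the text.** A false association requires (i) that scan types are pooled without stratification, (ii) that scan type is related to artefact score, and (iii) that scan type is related to exposure or to the sensor value.

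- *(i) Pooling.* No section states it. Section III names a correlation but not the set of scans over which it is computed. One patient group for enrolment and one assessment form do not fix one pooled analysis. The form may record scan type; its items are not visible.
- *(ii) Scan type and artefacts.* Plausible, but the protocol gives no data. The sentence on relaxation says what is scored and why. It reads equally well within a single scan type and makes no comparison between types.
- *(iii) Scan type and exposure.* No section ties them. Environmental experiences depend on what is set up at the time and on what the subject chooses. If the choice is unrelated to scan type (say 45% exposed in each), then (22.5 × 0.30 + 22.5 × 0.05)/45 = 17.5% and (27.5 × 0.30 + 27.5 × 0.05)/55 = 17.5%: no difference.
- *(iii) Scan type and pulse.* The wearable section excludes MRI scans. It does not say that the devices are worn during CT or PET/CT, and no other section does. Its hypothesis, that pulse may indicate how likely motion is, fits a reading taken before the scan. Mixed in-scan and out-of-scan readings are therefore an inference.
- *Radar and infrared.* The radar exclusion covers every imaging examination, and infrared may be used during imaging with no limit by scan type. Neither differs by scan type.
- *Enrolment.* Exam type may influence who enters. That changes the case mix. By itself it creates no association between exposure and artefacts among those who did enter.

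**The case for a change.** The strongest contrary argument is that stratification can wait for the statistical analysis plan, but data collection cannot. If pulse were recorded inside the scanner for some patients and only outside it for others, no later analysis could recover a common pre-scan reading. Calling the analysis descriptive is no protection either, because a crude correlation or cross-tabulation is descriptive and can still be confounded. Nor does the list of validity threats name scan type.

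The second point is right, and so is the third. The first depends on in-scan recording in CT or PET/CT, which the protocol does not state. It also overlooks that wearables are introduced as a feasibility question, that forms and assessment procedures are to be refined over an initial phase of up to 25 subjects per environmental experience, and that the structured recording of artefacts is expected to be refined as well. Exposure might differ by scan type if scanner rooms are equipped differently, but that is conjecture. What stands is that scan type is a plausible confounder which the protocol leaves unnamed under a general heading it does include.

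**Conclusion.** The concern does not hold. Its arithmetic is sound: 7.6 points under the central assumptions, 3.0 to 17.7 points over the range, in either direction. But it measures the bias of a pooled analysis that the protocol does not specify, with a scan mix, artefact rates and exposure rates that are all assumed. On the correlation scale the spurious value runs from 0 to about 0.20, the upper end needing shifts of a full standard deviation in both variables. With shifts of half a standard deviation or less in both, nominal significance would occur in about 5–9% of studies of 100 patients, against 5% by chance.

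The protocol is openly exploratory and descriptive, lists confounding among the threats it will assess, and leaves the choice of analysis to later statistical advice. Whether to show Aim 3 by scan type is ordinary content of a statistical analysis plan, and none is at hand to judge. Assigning environments at random would redesign a study built on the subject's choice. The conclusion would change only if a document fixed a pooled analysis, or stated that wearables are read during CT or PET/CT and combined with MRI patients' out-of-scan readings.

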Protocol Title: Assessing environmental factors in healthcare facilities in order to improve the experience of patients, staff and the quality of imaging procedures

Protocol Project Number: RP0525

Protocol Date: November 20, 2017

Principal Investigators:

[name], PhD
Professor and Novartis Chair of Imaging Research,
Vice Chairman of Research
Department of Radiology
The Ohio State University Wexner Medical Center
[name]
[name]
[contact]
[contact]
E-Mail: [contact]

I. Overview

In this exploratory study, we want to investigate how environmental factors such as light, sound, temperature, smell and sensory experiences such as vibration are being perceived by subjects in order to develop environmental strategies using those components to create a more relaxing, comforting experience for patients prior, during and after an imaging examination as well as for staff working in such environments.

We plan to include **volunteer participants** that complete survey tools and provide feedback on environmental experience, patients scheduled for imaging examinations, accompanying individuals of **patients** receiving care in the local environment, and **staff** working in healthcare environment.

In the subpopulation of patients that receive imaging examinations, we want to correlate observational findings and perception of environmental factors with image quality of the imaging examination performed with patient-based feedback on responses.

The goal of these exploratory efforts will be to serve as guidance to develop confirmatory clinical trials that eventually may facilitate and/or encourage refinements of facility environments and patient staff facility interactions to further improve the healthcare experience and quality of imaging examinations.

II. Objectives

- Aim 1:** To assess subjects' perceptions of environmental conditions and their preferences
- Aim 2:** To expose subjects to varied environmental conditions and to assess their perception and feedback
- Aim 3:** To explore potential patterns, factors of influence, points of reference in relation to the objectively assessed quality of an imaging examination and/or the perception of the patient
- Aim 4:** To explore the feasibility of innovative biofeedback, bio sensing and response capturing methodologies and technologies in order to guide the design of specific clinical investigations or trials

III. Background and Rationale

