Participants who have completed the general online survey by a specific date will have the opportunity to submit their email address at the end of the survey to be entered into a raffle for a chance to win one of five \$20 gift cards. This email will only be kept on record to determine the winners and will not be linked to their answers to the survey. These winners will be selected at random using a random number generator and will then be emailed to the winning participants after the date indicated on the survey.

Enrollment and participation choices**Online survey tool (virtual participation)**

As this survey will be openly accessible, we will not place any restriction on the number of participants but plan to close the survey once we have reached 1000 responses. We would like to achieve a broad participation and would be delighted to have responses in the range of 100 – 1000. This survey is identified below and labeled as the general survey.

Environmental experience (physical participation)

We anticipate a 20% rate of incomplete data or dropouts, so we request an initial total enrollment approval of 500 subjects. Of the 500 subjects, we intend to enroll 125 staff members, 125 patients, and 250 volunteers. We intend to use survey tools to assess the perception and preference of different environmental components. Subjects may participate in multiple experiences within a single session.

Subject participation choices

Subjects will be classified according to their type of participation into the three categories of volunteer, OSU staff or patients. In order to be eligible for the study, all subjects must complete an informed consent form. Patients, additionally, may complete the imaging examination experience during their imaging procedure. The table below summarizes the options given to the subject and reflects those that are included in the informed consent form.

Dependent on the implementation and testing set up available, subjects will be given the choice to participate in up to six environmental experiences. While the research staff will identify to the subject which environmental experience will be available, subjects have the choice to only select those in which they are willing to participate.

In addition to the survey tools, we will be potentially using additional observational tools such as infrared camera, radar and or wearable devices.

Subject Type	Participation
Volunteer	
WCIBMI Staff	
Patient	
Choices	
Survey only	
Facility Experience	

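### Does reading motion artefacts as a sign of relaxation fail if vibration or voice commands are active during the scan?

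*Protocol*

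**What the plan says.** Under IV. Procedures, Sample, Patient population (item 4), patients who complete a survey either take part in specific experience testing or "may be exposed to an environment experience during the imaging examination". The next sentence has the exam assessed for "quality factors such as motion artefacts as an indicator of being relaxed during the examination". Item 4 does not limit which experience may run during the scan and attaches no exception to this reading of motion.

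Other parts of the protocol bear on the point:

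- The Overview lists vibration among the components to be used "to create a more relaxing, comforting experience for patients prior, during and after an imaging examination".
- Subject participation choices says "subjects will be given the choice to participate in up to six environmental experiences" and adds: "Patients, additionally, may complete the imaging examination experience during their imaging procedure". The table that follows lists vibration and "Voice activation" among the six.
- Short wave radar bars radar during the imaging examination, and Wearable devices bars wearables during MRI. Vibration and voice carry no such bar.
- The Imaging Assessment Survey is described as "The survey completed by imaging assessors to determine the level of motion artefacts present in the images". The section on quality review of the imaging study describes the review as blinded and has the reader record presence and severity, in structured and free-text form.
- Background and Rationale gives the use of the data: "we want to correlate observational findings with image quality of the imaging examination performed and with patient based feedback on responses".

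**The concern.** A vibrating surface can move the patient, and so can speaking a command. If either happens during acquisition, the image may show motion that says nothing about how relaxed the patient was. Read literally, item 4 would count that motion against relaxation, so the stimulus under study could produce the very signal taken as its failure.

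The blinding sharpens the worry. A reader who does not know what was active cannot attribute the motion, however well the reading form is designed.

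At stake is the planned correlation of image quality with observations and patient feedback. Artefact unrelated to feedback pulls that correlation towards zero. Because the study is meant to guide confirmatory trials, a later trial sized on the weakened correlation would be larger than it need be. A natural remedy would be to keep scans with vibration or voice active out of the relaxation summary.

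**Working it through.** **What the text commits to.** The protocol states no figure on this point, so there is none to reproduce. The condition has to be read from the text:

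- Vibration perception gives the first implementation as a massage chair and mentions blankets only as a possibility. It refers to an imaging table or bed but not to a running scan.
- Voice activation says that feasibility in the imaging setting is being evaluated. It does not say that commands will be spoken during acquisition.
- Use during a scan is therefore neither stated nor excluded.

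**How large the effect could be.** Every rate here is an assumption.

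- p = artefact rate otherwise (10% to 30%)
- s = share of scans with vibration or voice active (1/6 to 1/3, borrowed from two of six listed options; a menu is not an exposure rate)
- m = share of those scans that gain an artefact from the stimulus (10% to 50%)
- q = s × m

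Take artefact as present or absent, and stimulus artefact as independent of feedback. The covariance with feedback then shrinks by (1 − q) and the artefact rate becomes p + q − pq. The share of the correlation that is kept is

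k = √[p(1 − q) / (p + q − pq)].

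The scans needed to detect the association scale as 1/k². Excluding the active scans restores the correlation but leaves a fraction 1 − s of the scans, so the scans needed scale as 1/(1 − s).

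At p = 0.20:

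| s | m | q | k | Dilution, 1/k² | Exclusion, 1/(1 − s) |
|---|---|---|---|---|---|
| 1/6 | 0.2 | 0.033 | 0.924 | 1.17 | 1.20 |
| 1/3 | 0.2 | 0.067 | 0.858 | 1.36 | 1.50 |
| 1/3 | 0.3 | 0.100 | 0.802 | 1.56 | 1.50 |
| 1/3 | 0.5 | 0.167 | 0.707 | 2.00 | 1.50 |

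For the last row: 0.2 × 0.833 / (0.2 + 0.167 − 0.033) = 0.167/0.333 = 0.50, and √0.50 = 0.707.

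Over the whole assumed range, k runs from 0.577 (p = 0.1, s = 1/3, m = 0.5; 3.0 times the scans) to 0.973 (p = 0.3, s = 1/6, m = 0.1; 1.06 times).

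**Break-even for exclusion.** Setting 1/k² = 1/(1 − s) gives m = p / [1 − s(1 − p)]. At p = 0.20:

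- s = 1/6: 0.2/0.867 = 23%
- s = 1/3: 0.2/0.733 = 27%

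Below those stimulus-artefact rates, dropping the scans loses more than the dilution does. The standard error rises by 1/√(1 − s), which is 1.095 and 1.225.

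**Scale in this study.** The protocol plans 125 patients and expects 20% incomplete data or dropout. If that rate applies to patients and each gives one scan, 125 × 0.8 = 100 scans remain. Suppose a true correlation of −0.288 (assumed). Its standard error is about (1 − 0.288²)/√100 = 0.09. The four cases move it to −0.266, −0.247, −0.231 and −0.204, which are shifts of 0.022, 0.041, 0.057 and 0.084. Each is smaller than one standard error.

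**The case for a change.** The strongest case for a change is that the protocol itself fixes what the measure means, and fixes it broadly, so this is not simply analysis detail left for later. The authors considered which devices may run during imaging, since they barred radar and, for MRI, wearables, yet they said nothing on vibration or voice. They also accept that motion can have other causes: Temperature monitoring checks whether temperature explains it. The Confounding paragraph is generic. Because the reader is blinded, the active experience has to be recorded at the session, and one data field per scan costs almost nothing. Independence may also be the mild case. If vibration improves feedback while adding artefact, the correlation could be pushed further towards zero or change sign.

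Much of this stands. The ambiguity is real, no passage deals with it by name, and knowing what was active during each acquisition is worth having. What does not follow is that the plan is wrong:

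- Item 4 names motion as one example among quality factors in a description of a population. It does not say how any artefact is to be scored.
- The protocol does not assume that exposure can only improve images. Its patient risk section allows that participation may worsen image quality.
- Choice of experience appears in the participation table, the quality review section expects structured recording to be refined, and Testing procedures and data recording plans iterative revision of forms for up to 25 subjects per experience. The forms themselves are not shown and may already hold the field.
- The Confounding paragraph, though general, names this kind of problem: an observation that relates to another manipulated variable.

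**Conclusion.** No change to the plan is needed. The possible misreading is conditional on a use of vibration or voice that the protocol neither states nor rules out, and it is nil if no such scan occurs. Where such scans do occur, a sensible analyst would show motion artefacts overall and by active experience before interpreting them. Section D. Data Analysis limits the work to descriptive statistics and promises biostatistical advice before anything more definitive, so no error rate or stated sample size is affected.

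The document supports no particular size for the effect. The worked range (58% to 97% of the correlation kept) rests on assumed rates, a present-or-absent artefact although severity is also recorded, and independence from feedback. The larger confirmatory trial is hypothetical, since nothing says that one would be sized on this correlation.

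Excluding the affected scans from the relaxation summary is a trade-off between bias and precision. It is the worse choice for detecting the association in two of the four cases at a 20% artefact rate. It would also remove some of the scans in which an experience was tested during imaging, the setting that Aim 3 is about.
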